5.6 Archiving

Trial documentation and data (including personal data) will be archived for at least 5 years after completion of the trial.

6 STATISTICAL ANALYSIS

6.1 Power and sample size

Following methods outlined by Chen at al.(67) we performed a scoping review of papers reporting KOOS4 in patellar dislocation. This identified 10 studies (non-surgical and surgical treatment) from which the 80th centile of the standard deviation (SD) was determined to give a conservative estimate of 21 for the SD. Based on the feasibility study and data from other orthopaedic studies within our unit, we assume that follow-up data are correlated with those collected at baseline (within person similarity). We conservatively estimate the correlation coefficient (ρ) as 0.5 for the KOOS4 at 18-months follow up. By explicitly including this adjustment in the sample size calculation, we reduce the effective SD from 21 to 18.2

We anticipate that there will be treatment switching between allocation groups in this pragmatic design. Hence, the choice of target difference should reflect any potential dilution of the observed treatment effect in the primary intention to treat (ITT) analysis. Therefore, reducing the between group target difference in KOOS4 score from 10 to 8-points (an effect size of 0.44) represents an important worthwhile difference for this design and population.

For a two-group parallel arm design, 90% power and 5% significance, we require data on 110 participants in each group. Allowing for an anticipated 20% loss to follow-up **results in a target sample size of 276 participants**. In this competency-based trial, each site will contribute small numbers and inflation for clustering is not necessary.

6.2 Planned recruitment rate

We estimate recruitment of 12 participants per year from the primary centre and four high recruiting centres, and six to nine participants per year from other centres, reflecting our feasibility experience. Based on 16 to 20 UK sites with a staggered start of two sites/month, recruitment will take 24 months. We have based recruitment rates on current practice but expect this strategy to improve recruitment beyond this.

6.2.1 Stop-go criteria

The first nine months of randomisation will act as an internal pilot, with a green target of 61 randomised, based on staggered opening of sites over the first year of recruitment (Table 4).

We will apply stop-go rules with the same percentage thresholds as used for ARTISAN and RACER-Knee (NIHR HTA 13/84/10 & 128768). In addition, thresholds for adherence with Personalised Knee Therapy and between-group time to intervention (randomisation to either first physiotherapist consultation for Personalised Knee Therapy or surgery) will be set. We have included a criterion for crossover to monitor the potential impact of this on our sample. The criterion for time to intervention has been chosen to ensure that both groups have fully recovered before the 18-month primary outcomes time-point.

If the study meets amber criteria, we will inform the TSC, review processes, look to open additional sites or amend trial processes, and review again in six months, particularly reflecting the nature that crossover may occur at any point post-randomisation. If the red criteria are met, we will discuss stopping the trial with the TSC and funders.

Table 4. Stop Go Criteria

	Red	Amber	Green
% Threshold			
Trial recruitment	< 66%	≥ 66%	≥ 100%
Recruitment rate/site/month ^a	< 0.5a	0.5 – 0.75a	≥ 0.75a
Number of sites opened	< 8 sites total	8 – 16 sites	16 sites
Total number of participants	< 40	40 - 61	= 61
recruited			
Non-adherence with	>30%	1 - 30%	0%
Personalised Knee Therapy ^b			
planned sessions			
Surgery date within 12-months	<70%	70 - 99%	100%
of randomisation ^b			
Crossover by 12-months ^b	20%	0 – 20%	0%

^aThis figure is a mean (x) across sites, individual sites will be variable in recruitment due to current referral patterns (Range 1.2-0.25 per site per month). ^bThese criteria will formally be assessed when the internal pilot participants have completed the 12-month time point but will be monitored monthly across the study so that early problems can be identified and addressed.

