2.7 Randomisation

2.7.1 Randomisation

Participants will be randomly allocated to the two treatment groups via a central computer-based randomisation system provided by the WCTU's programming team, independent of the study team. This will be performed after consent has been obtained and baseline data have been collected. This can happen on the same day as long as all processes occur pre-randomisation.

Randomisation will be in a 1:1 ratio using a minimisation procedure with a random factor of at least 70%, stratified by age group (<22/≥22), site of recruitment, and presence of patella alta in the study knee (defined by the presence of either a Biedert patella-trochlea overlap

ratio <0.25 on cross sectional imaging or Caton-Deschamps >1.2 on lateral radiograph/other routine clinical imaging/clinical judgement).(47-49)

Randomisation will be performed by any member of the local clinical or research team delegated to do so, using the online system. In the event that the online system is not working, sites should contact the study team on working days during working hours for guidance. As randomisation is not time critical in the REPPORT trial, waiting until the next working day is not a problem.

Stickers, electronic tags, or equivalent may be used on the participant's clinical notes to flag their eligibility and inclusion in the trial, depending on local site arrangements for flagging inclusion in trials.

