6.3.1 Statistical analysis principles

Treatment effects will be presented with appropriate 95% confidence intervals (where relevant), for all analyses. Tests will be two-sided and considered to provide evidence for a statistically significant difference if p-values are less than 0.05 (5% significance level). All analyses will be conducted following the ITT principle unless specified otherwise.

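### Table 4's stop-go bands overlap and leave values unassigned, and its separate crossover and surgery-timing limits are not tied to the dilution implied by cutting the target from 10 to 8 points

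*Protocol*

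**What the plan says.** Section 6.1 takes an SD of 21 and a baseline correlation of 0.5: "we reduce the effective SD from 21 to 18.2". It expects treatment switching to dilute the intention-to-treat effect and answers by "reducing the between group target difference in KOOS4 score from 10 to 8-points", which it also calls a worthwhile difference. It then states: "For a two-group parallel arm design, 90% power and 5% significance, we require data on 110 participants in each group". Allowing 20% loss to follow-up gives 276. No switching rate is given.

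Section 6.2.1 explains the crossover row: "We have included a criterion for crossover to monitor the potential impact of this on our sample". The relevant rows of Table 4 are:

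| Row | Red | Amber | Green |
|---|---|---|---|
| Crossover by 12 months | 20% | 0 – 20% | 0% |
| "Surgery date within 12-months" of randomisation | <70% | 70 – 99% | 100% |
| Participants recruited | <40 | 40 – 61 | = 61 |
| Sites opened | <8 | 8 – 16 | 16 |
| Recruitment per site per month | <0.5 | 0.5 – 0.75 | ≥0.75 |

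Amber leads to informing the TSC, a process review and a second look in six months. Red leads to a discussion about stopping with the TSC and funders. The footnote has the crossover and surgery-timing rows formally assessed once pilot participants reach 12 months, with monthly monitoring throughout. The primary outcome is KOOS4 at 18 months (section 3.1.1.1). Section 2.8.2 classes an operation that does not take place as non-compliance. The protocol does not say whether that also counts as crossover.

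**The concern.** There are two separate problems.

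First, a stop-go table is a decision rule, so each possible value should fall in exactly one band. Here several values fall in two bands and others in none, and one of the affected cells is the trigger for discussing whether to stop.

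Second, the crossover row is justified by its effect on the sample, and the only place where the sample size allows for switching is the step from 10 to 8 points. Contrast can be lost by two routes: participants allocated to Personalised Knee Therapy (PKT) who are operated on, and participants allocated to surgery who are not. Table 4 looks at these through two separate rows, each with its own amber range, both ending at month 12 although the outcome is at month 18. No figure shows the two together. Both rows could be amber while the expected intention-to-treat difference is below the 8 points on which the 90% power rests, and nothing in the table would show it.

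**Working it through.** **1. Bands read literally.**
- Crossover: 0% is amber and green; 20% is red and amber; above 20% has no band.
- Participants: 61 is amber and green; above 61 has no band.
- Sites: 16 is amber and green; above 16 has no band. Section 7.2.1 reports 27 sites, so values above 16 do occur.
- Rate per site: 0.75 is amber and green.

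A greater-than sign may have been lost from the red crossover cell when the PDF was read. Restoring it would settle 20% and the values above it. It would not settle the overlap at 0% or those in the other rows.

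**2. Reproducing the sample size.** The test is two-sided at 5% (section 6.3.1) with 1:1 allocation (section 2.7.1).
- Effective SD = 21 × √(1 − 0.5²) = 18.19, stated as 18.2. Effect size = 8 / 18.2 = 0.44.
- n per group = 2 × (1.960 + 1.282)² × (18.2 / 8)² = 108.8, so 109 by the normal approximation. The t test gives power 0.8981 at 109 and 0.9007 at 110, so 110 is right.
- 110 / 0.8 = 137.5, rounded up to 138 per group, 276 in total.

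The stated design reproduces.

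**3. Allowance implied by 10 to 8.** Assume linear dilution (my assumption; the protocol gives no model): ITT difference = 10 × (1 − a − b), where a and b are the shares of the PKT and surgery arms that lose the whole contrast. Setting this to 8 gives a + b = 0.20, for example 20% + 0% or 10% + 10%.

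**4. Power at 110 per group, SD 18.2.** Normal approximation: Φ(d / (18.2 × √(2/110)) − 1.96), where 18.2 × √(2/110) = 2.454.

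| Combined loss a + b | Difference | Power (normal) | Power (t) |
|---|---|---|---|
| 20% | 8 | 0.9032 | 0.9007 |
| 30% | 7 | 0.8139 | 0.8105 |
| 40% | 6 | 0.6861 | 0.6823 |
| 50% | 5 | 0.5309 | 0.5273 |

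**5. Both rows at their amber limit.** Take 20% crossover as full loss and 30% without surgery by 12 months. Let f be the fraction of the contrast that the 30% lose, and count nobody twice: difference = 10 × (1 − 0.20 − 0.30f).

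| f | Difference | Power (normal) |
|---|---|---|
| 0 | 8.00 | 0.90 |
| 0.25 | 7.25 | 0.84 |
| 0.5 | 6.50 | 0.75 |
| 0.75 | 5.75 | 0.65 |
| 1 | 5.00 | 0.53 |

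If the rows overlap fully, so that every crossover is a surgery-arm participant already among the 30%, the combined loss is at most 30%: 7 points and 81%. Surgery timing at its amber limit with no crossover and full loss gives the same 7 points and 81%.

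**The case against.** The strongest reply is that the power figures rest on a model that the protocol does not contain. Three stronger readings are tempting, and the documents support none of them.

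- **That the protocol budgets for 20% switching, so its 90% power is wrong.** Section 6.1 states no rate. Power of 90% for an 8-point intention-to-treat difference is correct whatever the switching. The 20% is an inference from 10 to 8.
- **That Table 4 lets the trial run on at 53% power.** The 20% and 30% cannot simply be added. The surgery row is a timing criterion: someone operated on in month 13 fails it but may gain some benefit by month 18, and crossover is undefined, so one person could count in both rows. Amber is not permission either; it brings TSC notification and a second review. The trial also compares initial strategies with later surgery accepted (section 1.2.1), so a switcher need not take on the outcome of the treatment received.
- **That crossover above 20% can never be red.** The evident intention is that it is red, and a sign may have been lost in PDF reading.

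These replies stand, and they limit the claim. Two things survive them. The other overlaps remain. Late surgery also matters on the protocol's own reasoning: the timing criterion is there so that both groups have recovered before 18 months, and section 2.8.1.2 expects recovery to plateau at around six months.

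**Conclusion.** The point holds and is of moderate weight. Table 4 needs correcting whatever view is taken of dilution, because several values have two bands or none. The power part is conditional. If 10 to 8 reflects linear dilution, it allows about 20 percentage points of lost contrast over both arms, and the two amber ranges can together exceed that. With complete loss, power is 81% at 30 points, about 68% at 40 and 53% at 50. At both amber limits the range is 53% to 90%, with 53% the worst case. These figures assume an undiluted difference of 10 points, SD 18.2, 110 analysed per group and crossovers counted as losing the whole contrast. The sample size arithmetic itself is sound.

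**What to change.** 1. **Table 4.** Make every row mutually exclusive and exhaustive. For example: crossover red >20%, amber >0% to 20%, green 0%; participants red <40, amber 40–60, green 61 or more; sites red <8, amber 8–15, green 16 or more; rate amber 0.5 to below 0.75. Define crossover, with its arm and denominator.
2. **Monitoring.** Keep the surgery-timing row, which has its own stated purpose. Add one figure for combined loss of contrast: the percentage of the PKT arm operated on plus the percentage of the surgery arm not operated on, each person counted once and followed to 18 months. Read it against the 10-to-8 allowance, not as an automatic stopping rule.
3. **Section 6.1.** State the switching assumption behind 8 points, and give power at higher combined switching (about 81% at 30%, 68% at 40%).

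The cost is rewording of section 6.1 and Table 4, plus one extra line in the monitoring reports, drawn from surgery data that the trial already collects. No extra participants are needed. The change restores no power; it makes the stated 90% openly conditional.

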6.3 Statistical analysis of effectiveness and harms

A detailed Statistical Analysis Plan (SAP) will be written by trial statisticians in line with Warwick SOP 21. The final version will be shared with the CI, the TSC and the DMC prior to the primary analysis taking place. The final analysis report will be reported in line with the CONSORT guidelines.(41, 68)

6.3.1 Statistical analysis principles

Treatment effects will be presented with appropriate 95% confidence intervals (where relevant), for all analyses. Tests will be two-sided and considered to provide evidence for a statistically significant difference if p-values are less than 0.05 (5% significance level). All analyses will be conducted following the ITT principle unless specified otherwise.

6.3.1.1 Summary of baseline data and flow of patients

Descriptive statistics will be constructed for baseline data to check for any characteristic differences between allocation groups. Graphical summaries will be created to aid interpretation of key results. A CONSORT chart illustrating participant flow throughout the study will also be produced.

6.3.1.2 Primary outcome analysis

The primary outcome will be analysed on an ITT basis and in line with the superiority design of the study. The primary model will be a generalised linear model used to assess differences in the KOOS4 score between treatment groups at 18-months post randomisation. At a minimum the model will include terms for allocation, age, sex, recruitment site, presence of patella alta and baseline KOOS4 score. If other important baseline variables are identified, they may be fitted as appropriate. Fitting a random effect for site effects will also be explored.

6.3.1.3 Secondary outcome analysis

Secondary outcomes will be analysed using a similar approach as appropriate to data and distribution. Categorical outcomes will be analysed with similar structure of models but with proportional logistic regression models.

6.3.1.4 Subgroup analyses

Pre-specified sub-group analyses will be undertaken to explore whether the intervention effect differs between:

- Age group (<22 or ≥22)
- Presence of patella alta (yes/no)

The subgroup analyses will follow the methods described for the primary analysis, with additional interaction terms incorporated into the mixed-effects regression model to assess the level of support for these hypotheses.

The study is not powered to formally test these hypotheses, so they will be reported as exploratory analyses only, and as subsidiary to the analysis reporting the main effects of the intervention in the full study population.

6.3.1.5 Sensitivity analyses

The primary inferences will be drawn from the models outlined under the ITT principle for the trial intervention of the *initial treatment strategy*. However, treatment switching is an important consideration in this study and other analysis populations will be used for exploratory analysis. An "as-treated" population, defined by the actual treatment received (i.e., those who underwent surgery and those who adhered to Personalised Knee Therapy) will be conducted. Per protocol analysis, restricted only to participants who adhere to protocolised treatment, will also be conducted to assess impact of protocol non-adherence. More details are given in the SAP.

The results of any exploratory analysis in non-ITT populations will be interpreted with caution because bias from confounding can be introduced by moving participants from their randomised group.(69)

6.3.1.6 Exploratory analyses

Exploratory models will be investigated to assess the change from pre-intervention scores to the 18-month outcome. This may include the use of latent growth models to assess trajectories of recovery.

6.4 Procedures to account for missing or spurious data

Missing data will be scrutinised and where possible, the reason for missingness recorded. If appropriate, multiple imputation methods in statistical software will be used. Any imputation methods used for scores and other derived variables will be carefully considered and justified. Consistency between cost-effectiveness and clinical effectiveness models will be explored and implemented where appropriate.

The results of the primary outcome model will not include the use of imputed datasets, but a sensitivity analysis using fully imputed datasets would be considered as an appropriate sensitivity analysis in comparison with the primary outcome model.

6.5 Health economic evaluation

A prospectively planned economic evaluation will be conducted from a NHS and personal social services perspective, according to the recommendations of the NICE reference case.(70) Details of the prospective plan and analysis will be described in the Health Economics Analysis Plan (HEAP) written by the trial health economists in line with guidance from Warwick SOP 21.

Health service contacts, made in connection with their treatments at six, 12, 18, and 24-months, will be recorded as part of the resource utilisation questionnaires. Time lost from school, college, university, or work (paid/unpaid), will also be recorded. Participants will be encouraged to use an electronic or paper calendar to help recall this information at follow-up. Intervention and sequelae healthcare resource use will be recorded and costed using most recently available UK published national reference costs, reflated to a common year.(71, 72)

Generic HRQoL will be assessed at baseline, three, six, 12, 18 and 24 months using the EQ-5D-5L questionnaire. EQ-5D-5L scores will be converted to health status scores using the UK value set recommended by NICE guidance at the time of analysis.(73) Using the trapezoidal rule, the area-under-the-curve of health status scores will be calculated, providing patient-level QALY estimates. Quality of life years (QALYs) will be estimated for the whole cohort, applying UK values.

If missingness of patient-level costs or QALYs ≤ 5%, the primary analysis will use complete case data.(74) If missingness exceeds 5%, mechanisms of missingness of data will be explored and multiple imputation methods will be applied to impute missing data. Complete case data or imputation sets will be used in bivariate analyses of costs and QALYs to generate within trial incremental cost per QALY estimates and confidence intervals.(75-78) Findings will be analysed and visualised as cost-effectiveness acceptability curves, net monetary benefit, and value of information analysis. Pre-specified sensitivity analysis will be used to explore the robustness and generalisability of findings.

The within trial analysis will serve as the primary analysis under several conditions reflected in the pattern of incremental costs and QALYs over the 24-months of follow-up: if these converge (no longer-term difference between interventions) or if they diverge such that either Personalised Knee Therapy or surgery are clearly dominant (with further extrapolation uninformative). If further modelling is likely to be informative, then the modelled finding will form the primary analysis. We will develop a decision analytic model, using our expertise in economic modelling in knee surgery.(79-81) The probabilistic model is likely take the form of a Markov model, capturing subsequent surgery including primary and revision knee replacement over the life course, with parameters drawn from published sources.(82, 83) Reporting will follow the Consolidated Health Economic Evaluation Reporting Standards (CHEERS) statement.(84)

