Follow-up	Primary outcome: 18-months after randomisation. Secondary timepoints: Six, 12, 18 and 24-months post randomisation.	
Planned Trial Period	From: 1 st January 2023 To: 31 st December 2027	
	Objectives	Outcomes
Primary	Clinical Effectiveness: To compare the clinical effectiveness of Personalised Knee Therapy versus patellofemoral surgical care at 18-months post randomisation.	Participant reported function at 18-months using the Knee Injury and Osteoarthritis Outcome 4-domain Score (KOOS4).
	Cost Effectiveness: To compare the cost-effectiveness of Personalised Knee Therapy against patellofemoral surgical care from an NHS and personal social service (PSS) perspective.	Base-case within trial analysis of cost per quality-adjusted life-years (cost/QALY).
Secondary	To quantify and draw inferences on pain, function, instability, dislocations, health utility, social participation, resource use,	All assessed at six, 12, 18, and 24-months unless specified otherwise.

occupational status, further surgery, KOOS4 (secondary and adverse events at six, 12, 18 outcome at six, 12 and 24months only) and 24-months after randomisation. The five individual KOOS domains (symptoms, pain, activities of daily living, sports, quality of life) Norwich Patellar Instability (NPI) Score Health-related quality of life (EQ-5D-5L) Work or education status (time off, change to status) Social activities (PROMIS Satisfaction with Social Roles and Activities 4a Short Form) Satisfaction with treatment Patient global impression of change (single item) Patellar dislocation events Adverse events including surgical complications Further knee surgery (either arm) Resource use **Process** Days from randomisation to treatment initiation. Measure Physiotherapy (PKT and post-operative rehabilitation) and surgical CRFs to assess intervention fidelity including information on: Number of physiotherapy sessions offered and attended Composition of physiotherapy attended Participant CRFs to assess intervention adherence, including information on number of physiotherapy sessions attended, at six, 12, 18 and 24

months post-randomisation.

LIST OF ABBREVIATIONS/GLOSSARY

Abbreviation	Explanation
AE	Adverse Event
BASK	British Association for Surgery of the Knee
ВОА	British Orthopaedic Association
BOAST	British Orthopaedic Association Standards for Trauma and
BPFS	Orthopaedics British Patellofemoral Society
CHEERS	Consolidated Health Economic Evaluation Reporting Standards
CI	Chief Investigator

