2.2.1 Primary objectives

- To compare the clinical effectiveness of Personalised Knee Therapy versus surgery, based on participant reported function 18-months after randomisation, using the Knee Injury and Osteoarthritis Outcome 4-domain Score (KOOS4).
- 2) To compare the cost-effectiveness of Personalised Knee Therapy against surgery from an NHS and personal social service perspective.

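### The primary economic analysis is within-trial in Table 1, but section 6.5 lets a life-course model replace it depending on the observed 24-month results

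*Protocol*

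**What the plan says.** Cost-effectiveness is the second of two primary objectives in section 2.2.1: "To compare the cost-effectiveness of Personalised Knee Therapy against surgery from an NHS and personal social service perspective". That objective gives no time horizon. Table 1 (Trial Summary) pairs the same objective with the outcome "Base-case within trial analysis of cost per quality-adjusted life-years (cost/QALY"), unconditionally.

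Section 6.5 handles it differently. It states that "The within trial analysis will serve as the primary analysis under several conditions reflected in the pattern of incremental costs and QALYs" over the 24 months of follow-up. Two conditions are given. One is convergence: "if these converge (no longer-term difference between interventions"). The other is dominance: "if they diverge such that either Personalised Knee Therapy or surgery are clearly dominant (with further extrapolation uninformative"). The next sentence provides the alternative: "If further modelling is likely to be informative, then the modelled finding will form the primary analysis". The model is described as probabilistic, probably of Markov form, and "capturing subsequent surgery including primary and revision knee replacement over the life course, with parameters drawn from published sources".

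Sections 3.1.4 and 6.5 leave detail to a Health Economic Analysis Plan (HEAP), which is not at hand.

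**The concern.** A primary objective should lead to one named analysis, known before the comparison is seen. Here a reader of Table 1 expects the within-trial cost per QALY as the headline, while a reader of section 6.5 learns that the headline may be a lifetime model built on published parameters. What decides between them is the observed pattern of incremental costs and QALYs, which is the result itself.

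The two analyses can answer differently because their horizons and inputs differ. If the result determines which one is primary, the headline statement about value for money partly reflects that selection, and nothing in the reported uncertainty of either analysis shows it.

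**Working it through.** **1. The passages side by side.**

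| Place | Primary economic analysis | Condition |
|---|---|---|
| Section 2.2.1 | Cost-effectiveness, NHS and PSS perspective | No horizon stated |
| Table 1 | Within-trial cost per QALY, as base case | None |
| Section 6.5, missing-data rule | Primary analysis based on patient-level costs and QALYs, complete-case if missingness is at most 5% | Amount of missing data only |
| Section 6.5, closing paragraph | Within-trial | Observed convergence or clear dominance |
| Section 6.5, closing paragraph | Life-course model | Modelling judged likely to be informative |

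The second and third rows treat the within-trial analysis as primary. The last row allows something else. These statements cannot all hold.

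**2. What drives the switch.** The trigger is "under several conditions reflected in the pattern of incremental costs and QALYs over the 24-months of follow-up", a between-arm result. The protocol gives no numerical meaning for convergence, clear dominance or likely informativeness, and does not say who decides or when. The branches are also not complements. If the arms diverge without dominance and modelling is not judged informative, neither sentence assigns a primary analysis.

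**3. Can the horizon change the answer?** The protocol gives no figure from which this can be calculated, so what follows is an illustration. Assumed: £20,000 per QALY, a utility gain of 0.01, and 3.5% discounting over 40 years. From section 1.1.2: about £5M for about 2,000 operations a year.

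- Gross cost per operation: 5,000,000 / 2,000 = £2,500.
- Over 24 months, undiscounted: 0.01 × 2 = 0.02 QALY; 0.02 × 20,000 = £400.
- Over 40 years: annuity factor (1 − 1.035^−40) / 0.035 = 21.4; × 0.01 = about 0.21 QALY; × 20,000 = about £4,270.

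The gain is worth less than £2,500 on the short horizon and more on the long one. The £2,500 is a gross cost of surgery. The increment between arms would also depend on therapy costs, post-operative rehabilitation and later surgery in the therapy arm, so the comparison shows direction and scale only.

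**4. Can sampling error move the trigger?** Again an illustration. Assumed: 110 analysed per arm (the section 6.1 figure for KOOS4), QALY SD 0.3 to 0.5, cost SD £1,500 to £3,500, surgery truly dearer by £500 to £1,500. The standard error of a difference is SD × √(2/110), which is 0.040 to 0.067 QALY. The probability that the point estimates show one arm both cheaper and better is:

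| True QALY difference in favour of surgery | Probability of point-estimate dominance |
|---|---|
| 0 | about 50% |
| 0.02 | 31% to 42% |
| 0.05 | 11% to 31% |

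Point-estimate dominance is a looser criterion than clear dominance, so these are not the probabilities of the section 6.5 rule. They show that the pattern on which the rule relies is noisy at this sample size.

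**The case against.** The strongest defence is that section 6.5 sets out its rule beforehand, that the rule asks whether extrapolation adds information and not which arm it favours, and that the HEAP may define the terms. A long horizon also has a real rationale: section 1.1.1 describes osteoarthritis and long-term disability. Much of this stands. The absence of thresholds from the protocol is not in itself an error. But the HEAP cannot remove a conflict between Table 1 and section 6.5, and even well-defined thresholds would still let the results choose the headline analysis. The case for a long horizon supports always reporting the model, or naming it primary now.

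Three stronger readings are tempting and not supported:

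- **That the choice is post hoc.** A qualitative rule is stated in advance. It depends on the data and its terms are open, which is a lesser fault.
- **That the confidence intervals and acceptability curves become invalid.** Section 6.5 commits without condition to within-trial estimates and intervals, and these are calculated the same way whichever analysis is called primary. The protocol sets no error rate for the economic comparison.
- **That the illustration shows discretion reversing the conclusion.** The reversal comes from the horizon. A persisting gain with dearer surgery is neither convergence nor dominance, so section 6.5 would point to the model anyway. Reporting both analyses would show the same contrast. Nor do the documents support calling a 0.01 gain undetectable, since they give no SD for utility or QALYs.

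**Conclusion.** The point holds as an inconsistency in the definition of the primary economic analysis, together with a pre-stated, qualitative rule that makes the choice depend on between-arm results. It rests on the text alone and needs no assumed figure. It should be corrected because it concerns a primary objective and the correction is cheap.

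Its numerical effect cannot be derived from the documents. The £400 and £4,270 figures depend on the assumed threshold, on a 0.01 gain lasting 40 years and on comparison with a gross surgery cost, and should be read only as a sign that the horizon can matter. The KOOS4 primary analysis and the sample size are not touched.

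**What to change.** Name one primary economic analysis, in the same terms, in Table 1 and section 6.5 (and the HEAP), before any between-arm cost and QALY data are seen. Delete the sentence in section 6.5 that promotes the model according to the results, and the conditions placed on the within-trial analysis.

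- **Smallest change:** keep the within-trial analysis that Table 1 names, with the 24-month horizon of section 6.5, and always report the decision model as a pre-specified secondary analysis. Possible wording: *The primary economic analysis is the within-trial cost per QALY over 24 months. The decision model is secondary and will be reported whatever the within-trial result.*
- **If the sponsor prefers the longer horizon:** name the model primary now, amend Table 1, and always report the within-trial result beside it.

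Insisting on 24 months would be partly a preference; either choice resolves the problem if fixed in advance. The cost is a few sentences in the protocol and the HEAP, with no effect on participants or data collection. The downside is that one analysis carries the secondary label even where decision-makers prefer its horizon.
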